4.2.8.1 PRO-CTCAE

Data from the PRO-CTCAE will be summarised for those patients with evaluable data. The number (%) of patients with each level of response for each PRO-CTCAE item at baseline and over time will be summarised.

4.2.8.2 EORTC QLQ- C30 and EORTC QLQ- OV28

The EORTC-QLQ-C30 and EORTC-QLQ-OV28 questionnaires will be summarized. Descriptive statistics of absolute scores and change from baseline of all subscales will be presented and plots will be generated as appropriate to interpret changes over time.

Proportions of patients who had a best observed change of improved, stayed the same or deteriorated whilst on treatment (excluding follow-up) for all subscales (symptom and functioning scales) will be presented. A 10 point change in score will be used as cut-off point. Improved will be defined as the number (%) of patients with two assessments at least 18 days apart (i.e. 21 days allowing a visit window of 3 days) which showed a clinically meaningful improvement (a decrease from baseline score ≥ 10) in that symptom from baseline. The quantity and impact of missing data will be evaluated. If warranted, some investigation of HRQoL data by whether patients are still taking study drug will be performed.

Symptom Improvement Rate at 8 weeks

For dyspnea, pain and constipation from QLQ-C30 and abdominal/GI symptoms from QLQ-OV28, the symptom improvement rate at 8 weeks (follow-up data will be excluded) will be defined as the number (%) of patients showing a clinically meaningful improvement (a decrease from baseline score ≥ 10 ; Osoba et al 2005) in that symptom from baseline. The denominator will consist of a subset of the FAS population who have a baseline symptom score ≥ 10 . A 95% confidence interval for the symptom improvement rate will be constructed using the Clopper-Pearson method.

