Were you upset by the loss of your hair?	1	2	3	4
40. Did food and drink taste different from usual?	1	2	3	4
41. Have you had tingling hands or feet?	1	2	3	4
42. Have you had numbness in your fingers or toes?	1	2	3	4
43. Have you felt weak in your arms or legs?	1	2	3	4
44. Did you have aches or pains in your muscles or joints?	1	2	3	4
45. Did you have problems with hearing?	1	2	3	4
46. Did you urinate frequently?	1	2	3	4
47. Have you had skin problems (e.g. itchy, dry)?	1	2	3	4
48. Did you have hot flushes?	1	2	3	4
49. Did you have night sweats?	1	2	3	4

Please go on to next
page

During the past week:

	Not at All	A Little	Quite a Bit	Very Much
50. Have you felt physically less attractive as a result of your disease or treatment?	1	2	3	4
51. Have you been dissatisfied with your body?	1	2	3	4
52. How much has your disease been a burden to you?	1	2	3	4
53. How much has your treatment been a burden to you?	1	2	3	4
54. Were you worried about your future health?	1	2	3	4

During the past 4 weeks:

	Not at Very All	A Little Much	Quite a Bit	
55. To what extent were you interested in sex?	1	2	3	4
56. To what extent were you sexually active?	1	2	3	4

Answer the following two questions only if you were sexually active:

57. To what extent was sex enjoyable for you?	1	2	3	4
58. Did you have a dry vagina during sexual activity?	1	2	3	4

NCI PRO-CTCAE™ ITEMS

Item Library Version 1.0

As individuals go through treatment for their cancer, they sometimes experience different symptoms and side effects. For each question, please check or mark an in the one box, that best describes your experiences over the past 7 days...

1.	In the last 7 days, what was the SEVERITY of your DECREASED APPETITE at its WORST?				
	 None	 Mild	 Moderate	 Severe	 Very severe
	In the last 7 days, how much did DECREASED APPETITE INTERFERE with your usual or daily activities?				
	 Not at all	 A little bit	 Somewhat	 Quite a bit	 Very much

2.	In the last 7 days, how OFTEN did you have NAUSEA?				
	 Never	 Rarely	 Occasionally	 Frequently	 Almost constantly
	In the last 7 days, what was the SEVERITY of your NAUSEA at its WORST?				

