3.4 Patient reported outcomes

Patient reported outcomes will be assessed by EORTC-QLQ-C30, and EORTC-QLQ-OV28, according to the schedule listed in [Table 8](#). They will also be assessed using PRO-CTCAE.

The PROs will be collected (using an electronic diary) according to the following schedule and assessments will be mapped into scheduled visits using a windowing rule similar to other endpoints collected by visit:

Table 8 PRO Schedule

PRO Tool	Week 1-12	Week 12 - Progression	Post-progression until end of study
EORTC QLQ-C30	Day1, then every 8 weeks	Every 8 weeks	Day 30 follow-up
EORTC QLQ-OV28	Day 1, then every 8 weeks	Every 8 weeks	Day 30 follow-up
PRO-CTCAE	Day 1, then weekly	Every 4 weeks	Day 30 follow-up

An outcome variable consisting of a score from 0 to 100 will be derived for each of the symptom scales/ items, the functional scales and the global health status scale in the QLQ-C30 and for each of the symptom scales/items in the QLQ OV28 according to the EORTC QLQ-C30 Scoring Manual and EORTC QLQ OV28 instructions. Higher scores on the global health status and functional scales indicate better health status/function. Higher scores on the symptom scales indicate greater symptom burden.

The following endpoints will be used to assess the HRQoL:

- Absolute scores and change from baseline of all subscales
- Proportions of patients with a best observed change of improved, stayed the same or deteriorated for all subscales (symptom and functioning scales). A minimum clinically meaningful change is defined as a 10 point change in score from baseline.
- Best observed change of improvement will be defined as the number (%) of patients with two assessments at least 18 days apart (i.e. 21 days allowing a visit window of 3 days) which showed a clinically meaningful improvement (a decrease from baseline score ≥ 10) in that symptom from baseline.
- Symptom improvement rate at 8 weeks for dyspnea, pain and constipation from QLQ-C30 and abdominal/GI symptoms from QLQ-OV28.

Summary measures of overall compliance and compliance over time will be derived for the EORTC-QLQ-C30 and OV28 respectively. These will be based upon:

- Received questionnaire = a questionnaire that has been received and has a completion date and at least one individual item completed.

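### The best-observed-change table includes functioning scales, but the SAP writes 'improved' only as a decrease in score, which is the wrong sign for those rows

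*SAP*

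**What the plan says.** SAP 4.2.8.2 plans the proportions of patients whose best observed change on treatment was improved, stayed the same or deteriorated, and says that these "for all subscales (symptom and functioning scales) will be presented". SAP 3.4 lists the same endpoint with the same scope.

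Both sections define only one of the three labels. Improved requires a pair of forms, "two assessments at least 18 days apart (i.e. 21 days allowing a visit window of 3 days"). The direction comes next in the definition: each of the pair must be one "which showed a clinically meaningful improvement (a decrease from baseline score" of at least 10. SAP 4.2.8.2 then closes that sentence by tying the decrease to a symptom and moves on: "in that symptom from baseline. The quantity and impact of missing data will be evaluated".

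On score direction, SAP 3.4 states: "Higher scores on the global health status and functional scales indicate better health status/function". It says the opposite for symptom scales, where a higher score is a greater burden. The threshold is given without a direction: "A minimum clinically meaningful change is defined as a 10 point change in score from baseline". For OV28, SAP 3.4 says that scores are derived "for each of the symptom scales/items in the QLQ OV28" and refers to that module's scoring instructions.

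Protocol 8.4.2 names the three labels and a 10-point cut-off but gives no direction and no confirmation rule. SAP 6 corrects only a strict inequality in the 8-week symptom improvement rate.

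**The concern.** A decrease is the right direction of improvement for symptoms and the wrong one for functioning. The table covers both, so one rule with one sign cannot serve all its rows. Health-related quality of life is a secondary objective, and this is its responder table across all subscales. The study has a single arm, so no comparator column would make a reversed row stand out. A program that follows the definition literally would report patients who lost function as improved and leave out those who gained it.

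**Working it through.** No figure in the plan depends on this rule, so there is none to reproduce. The check sets the written rule against the SAP's own score directions.

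**1. The rule on example score paths.** The baseline and the two scores are invented for illustration. The two forms fall at days 57 and 113, which are 56 days apart, so the 18-day spacing (21 − 3 = 18) is met.

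| Scale type | Path | Changes | True course (SAP 3.4) | As written (decrease ≥ 10 twice) | Mirrored (increase ≥ 10 twice) |
|---|---|---|---|---|---|
| Functioning | 80 → 60 → 60 | −20, −20 | worse | improved | not improved |
| Functioning | 40 → 60 → 60 | +20, +20 | better | not improved | improved |
| Symptom | 60 → 40 → 40 | −20, −20 | better | improved | not applicable |

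The written rule is right for symptoms and reversed for functioning.

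**2. Rows affected.** SAP 3.4.1 gives 5 functional + 3 symptom + 1 global + 5 single items + 1 financial = 15 QLQ-C30 rows. The functional scales are 5 of 15 (33%), or 6 of 15 (40%) if global health is shown. SAP 3.4.2 gives 7 multi-item groups + 4 single items = 11 OV28 rows. Out of all 26 rows, that is 5/26 = 19%, or 6/26 = 23% with global health.

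**3. The two readings of the definition.**
- If it governs every row, the functioning rows have the wrong sign, and the two-assessment confirmation does apply to them.
- If its reference to a symptom limits it to symptom rows, the functioning rows have no written definition of improved, and so neither a sign nor a confirmation rule.

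Both cannot hold at once, but each leaves the functioning rows without a usable rule.

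**4. Patients with only one on-treatment form.** Improved needs two qualifying forms. These are 8-weekly (SAP Table 8), so the earliest confirmed improvement on schedule is week 16. Protocol 8.2 assumes a median PFS of 6 months, which is 182.6 days. My added assumptions are exponential PFS and forms ending at progression.

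- S(t) = 0.5^(t/182.6), so S(56 days) = 0.809 and S(112 days) = 0.654.
- If the form at the visit showing progression is not counted, the share with exactly one form is 0.809 − 0.654 = 0.155, or 9.3 of 60.
- If that form is counted, and deaths before week 8 are ignored, the share is 1 − 0.809 = 0.191, or 11.5 of 60.
- For a median of 4 months the two figures are 0.198 and 0.273. For 9 months they are 0.115 and 0.132.

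These patients cannot be improved on any scale, and the SAP does not say which label they receive.

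**The case against.** The strongest reply is that the definition speaks of a symptom, so it was never meant for functioning rows, and a competent programmer would take their direction from SAP 3.4. Most of this stands. The intended sign can be inferred, and absolute and change scores for all subscales are presented alongside, so an attentive reader could notice a reversed row. The reply still concedes that the rule for five or six rows is not written down, and the only sentence that starts to define improved points the other way.

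A reader might go further and infer that the plan leaves the order of the labels open, so that a single bad form could make a patient deteriorated. The documents do not support this. The variable is the best observed change, which ranks improved above stayed the same and that above deteriorated. A patient with one bad and one stable form is not deteriorated on a best-change rule.

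A reader might also infer that the OV28 sexuality scale is another reversed row, because the form asks "To what extent was sex enjoyable for you", where a higher answer is better. That cannot be established here. SAP 3.4 defers to scoring instructions that are not in the documents, and the next item on the form, on vaginal dryness, runs the other way. I do not count it.

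The single-form share also has a limit. The EORTC row of Protocol Table 5 shows a further form near the end of treatment, and its column cannot be read with certainty in the text available. If that form falls at discontinuation and counts as on treatment, some of these patients would have two forms.

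**Conclusion.** The point holds as a defect in a stated rule. Applied as written, 'improved' has the wrong sign for the 5 QLQ-C30 functional scales, or 6 with global health. On the narrower reading, those rows have no rule. No other text in the protocol or SAP repairs it. The direction of the fault rests only on the SAP's own statement of score direction.

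The size in percentage points cannot be derived, because the documents give no distribution for the change scores. The distortion could flatter or understate the treatment, depending on whether function tends to fall or rise.

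The labelling of patients with a single form or one unconfirmed change is a lesser matter of missing detail. It concerns about 15% to 19% of patients with one form at a 6-month median PFS (11% to 27% for medians of 9 to 4 months), under the assumptions given.

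A reader might infer that the HRQoL results as a whole are unreliable. That does not follow. The fault is confined to one descriptive secondary table. ORR, absolute and change scores, and the 8-week rate, which is restricted to named symptoms, are unaffected.

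**What to change.** In SAP 3.4 and 4.2.8.2, replace the single definition with one for each scale type:

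- **Symptom scales and items:** improved is a decrease of at least 10 from baseline; deteriorated is an increase of at least 10.
- **Functional and global health scales:** improved is an increase of at least 10; deteriorated is a decrease of at least 10. Say whether global health is a row of this table.
- **OV28:** take the direction of each scale from its scoring instructions and write it down.
- **Confirmation:** apply the two-assessment, 18-day requirement to improvement on every scale type.

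As clarification only, state that improved outranks stayed the same, which outranks deteriorated, and say how patients with one unconfirmed change or only one on-treatment form are labelled.

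The cost is a short paragraph in two SAP sections, ideally before the table is programmed. It needs no new data and changes nothing in the sample size or the primary analysis.

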4.2.9 Safety and tolerability

Safety and tolerability data will be presented using summaries and descriptive statistics.

The safety analysis set will be used for all safety and tolerability tables, figures and listings except where expressly noted.

For change from baseline summaries for vital signs, laboratory data, LVEF, the baseline value will be the latest result obtained prior to the start of investigational product.

The denominator used in laboratory summaries will only include evaluable patients, in other words those who had sufficient data to have the possibility of an abnormality. For example:

- If a CTCAE criterion involves a change from baseline, evaluable patients would have both a pre-dose and at least 1 post-dose value recorded.
- If a CTCAE criterion does not consider changes from baseline, to be evaluable the patient need only have 1 post dose-value recorded.

The denominator in vital signs data should include only those patients with recorded data.

REACT

To enable continuing assessment of the safety profile of the cediranib and olaparib combination, and toxicity management for study patients, a data visualisation tool (e.g., REACT) will be used. No efficacy data (RECIST response; progression status) will be included. The “CONCERTO principles for use of REACT” document will describe appropriate access to and use of the tool.

AEs

All AE data will be listed individually by patient. Any AE occurring before treatment with either IPs will be included in the data listings and flagged but will not be included in the summary tables of AEs.

An overview table will summarise the number and percentage of patients with at least one of the following AEs where patients with more than one AE in a particular category are counted only once in that category:

- Any AE
- Any AE causally related to either IP, listed separately
- Any AE of CTCAE grade 3 or higher
- Any AE of CTCAE grade 3 or higher, causally related to either IP, listed separately
- Any AE with outcome of death
- Any AE with outcome = death, causally related to either IP, listed separately
- Any SAE (including events with outcome=death)
- Any SAE (including events with outcome=death), causally related to either IP, listed separately
- Any SAE leading to discontinuation of either IP, listed separately
- Any AE leading to discontinuation of either IP, listed separately
- Any AE leading to discontinuation of either IP, listed separately, causally related to either IP, listed separately
- Any AE leading to dose interruption
- Any AE leading to dose reduction
- Any AE leading to dose modification (interruption and/or reduction)
- Any other significant AE (if applicable)

The number and percentage patients reporting each AE will be summarised, by SOC (sorted alphabetically) and PT (sorted by descending overall total) The following summaries will be produced:

- AEs by SOC and PT.
- AEs by maximum reported CTCAE grade, by SOC and PT.
- AEs of CTCAE grade 3 or higher, by SOC and PT.
- AEs causally related by IP, by SOC and PT.
- AEs leading to hospitalisation, by SOC and PT.
- AEs leading to dose interruption, by SOC and PT.
- AEs leading to dose reduction, by SOC and PT.
- AEs with outcome of death, by SOC and PT.
- AEs with outcome of death, causally related by IP, by SOC and PT.
- SAEs by SOC and PT.
- SAEs causally related by IP, by SOC and PT.

51(56)

- AEs leading to discontinuation of either IP (listed separately), by SOC and PT.
- OAEs by SOC and PT (if applicable).

In the above summaries, patients with more than one AE within a particular SOC are counted only once for that SOC. Similarly, patients with more than one AE within a particular PT are counted only once that PT. For summaries by maximum reported CTCAE grade with multiple AEs within a particular SOC or PT will be counted under the category of their most severe AE within that SOC or PT.

A summary of deaths will be provided, detailing deaths due to disease only, deaths where AE outcome is death only or both.

AEs of special interest

The AESIs for Cediranib are as follows: PRES, arterial thromboembolic events, and the Important Potential Risks: symptomatic left ventricular dysfunction and cardiac failure; nephrotic syndrome; renal thrombotic microangiopathy, liver failure, and (per eCRF) diarrhea, fatigue, hypertension and nausea. The AESIs for Olaparib are as follows: potential risks of MDS/AML, new primary malignancy (other than MDS/AML) and pneumonitis.

Grouped summary tables of certain MedDRA preferred terms will be produced and may also show the individual preferred terms which constitute each AESI grouping. Groupings will be based on preferred terms provided by the medical team prior to DBL, and a listing of the preferred terms in each grouping will be provided.

Summaries of the above-mentioned grouped AE categories will include number (%) of patients who have:

- At least one AESI presented by outcome
- At least one AESI causally related to either study medication separately
- At least one AESI leading to discontinuation of either study medication separately

A summary of total duration (days) of AESI will be provided for events which have an end date and this will be supported by summaries of ongoing AESIs at death and, separately, at data cut-off.

To reflect the particular interest in diarrhoea, fatigue, hypertension, and nausea, life tables and prevalence plots will be produced for these AEs.

In addition as all CTCAE grade changes for diarrhoea, fatigue, hypertension, and nausea will be recorded, a plot will be generated for each AE which shows the AE grade over time for each patient.

Laboratory evaluations

All laboratory data recorded in the eCRF will be listed. If any additional analyses to those in [Table 7](#) are also recorded then these will be listed only. Out-of-reference range values will be flagged as high (H) or low (L) in the listings.

For clinical chemistry and haematology, numerical summaries will be generated which include the mean, standard deviation, median, minimum value, maximum value, and lower and upper quartiles at each visit in which laboratory values are taken. Plots of both the maximum post-baseline ALT and AST versus the maximum post-baseline total bilirubin, expressed as multiples of their upper limit of reference range will be produced.

As a primary interpretation of potential drug induced liver injury, outputs related to patients with liver function tests (LFTs) that meet biochemical criteria for Hy's Law and with elevations of LFTs will be produced. Biochemical criteria for Hy's Law are defined as any situation where a study patient has an increase in both AST or ALT $\geq 3 \times \text{ULN}$ and TBL $\geq 2 \times \text{ULN}$, irrespective of ALP, at any point during the study. The elevations do not have to occur at the same time or within a specified time frame.

For all patients who meet the criteria for potential Hy's Law, a plot of AST, ALT, ALP and total bilirubin over time will be produced.

The proportion of patients who met GCIG criteria for CA-125 progression (any of the criteria, and each criterion individually) will be summarised by visit. The time to CA-125 progression will be presented using a Kaplan Meier plot and the median time to CA-125 progression (from the Kaplan Meier) calculated. Patients without CA-125 progression will be censored at their latest lab evaluation visit.

Vital signs

Absolute values and change from baseline will summarised, overall and by visit. The minimum, maximum, and most recent measurement will also be listed. Plots of observed and changes in vital sign variables data may be generated to illustrate the data.

Physical examination

Abnormalities identified from physical examination will be captured as AEs.

4.2.10 PK

PK data will be analysed and reported separately from the CSR, along with other studies as part of a pooled population PK analysis.

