6.3.2 Follow-up of unresolved adverse events

Any SAE or non-serious adverse event that is ongoing at the time of the 30-day follow up, must be followed up to resolution unless the event is considered by the investigator to be unlikely to resolve, or the patient is lost to follow up. AstraZeneca retains the right to request additional information for any patient with ongoing AE(s)/SAE(s) at the end of the study, if judged necessary.

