3.3.3 AEs

AEs and SAEs will be collected throughout the study, from date of first dose of either IP until 30 days after the last dose of study medication. The Medical Dictionary for Regulatory Activities (MedDRA)(using the latest MedDRA version available at database lock) will be used to code the AEs. AEs will be graded according to the National Cancer Institute Common Terminology Criteria for AEs (CTCAE Version 4.03).

If partial dates of onset occur, a conservative approach will be followed and events will be assumed to be treatment emergent unless there is convincing evidence to the contrary.

The following variables will be collected for each AE;

- AE verbatim
- The date when the AE started and stopped
- Changes in CTCAE grade will be reported for AEs of diarrhoea, fatigue, hypertension and nausea. For all other AEs, only the highest attained CTCAE grade will be reported.
- Whether the AE is serious or not
- Investigator causality assessment against each of the IP(s) (yes or no)
- Action taken with regard to each of the IP(s)
- Outcome (if resolved with sequelae then sequelae should be recorded).

In addition, the following variables will also be collected for SAEs:

- Date AE met criteria for SAE
- Date Investigator became aware of SAE
- AE seriousness criteria
- If the patient was hospitalized:
- Date of hospitalization
- Date of discharge

The following variables will also be collected for deaths:

- Probable cause of death
- Date of death
- Autopsy performed
- Causality assessment in relation to IPs and/or Study procedure(s).

Groups of preferred terms will be used to identify adverse events of special interests (AESIs); these preferred terms will be listed before database lock and documented in the Study Master File. The AESIs for cediranib will include PRES, arterial thromboembolic events, symptomatic left ventricular dysfunction and cardiac failure, nephrotic syndrome, renal thrombotic microangiopathy, liver failure, diarrhea, fatigue, hypertension and nausea. The AESIs for olaparib will include MDS/AML, new primary malignancy (other than MDS/AML) and pneumonitis.

For the purposes of this study all AESIs identified above will be reported for both IPs.

Any AE occurring before the start of IP or more than 30 days after discontinuation of IPs will be included in the data listings but will not be included in the summary tables of AEs.

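### The AESI duration table uses only events that have ended, so it understates how long persistent AESIs last; ongoing AESIs are reported separately but never enter the duration estimate.

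*SAP*

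**What the plan says.** In SAP section 4.2.9, under AEs of special interest, the duration statistic is limited to ended events: "A summary of total duration (days) of AESI will be provided for events which have an end date". The same sentence goes on: "this will be supported by summaries of ongoing AESIs at death and, separately, at data cut-off". It does not say whether those ongoing summaries give counts, elapsed time or both.

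SAP section 3.3.3 extends the cediranib AESI list to include "renal thrombotic microangiopathy, liver failure, diarrhea, fatigue, hypertension and nausea". For diarrhoea, fatigue, hypertension and nausea, section 4.2.9 adds two displays: "life tables and prevalence plots will be produced for these AEs", and "a plot will be generated for each AE which shows the AE grade over time for each patient". All AESI groupings also get a count of patients with "At least one AESI presented by outcome", and "All AE data will be listed individually by patient".

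On data capture, Protocol section 6.3.2 says that an event ongoing at the 30-day visit "must be followed up to resolution unless the event is considered by the investigator to be unlikely to resolve", with loss to follow-up as a further exception. Protocol section 3.9.1 adds the start of new anti-cancer treatment as an end to follow-up. Under section 3.10.1, AEs after withdrawal of consent are followed outside the study. SAP section 3.3.3 describes AE collection as running to 30 days after last dose.

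**The concern.** Whether an event has an end date depends on how long it lasts. An event that outlasts the patient's observation has none, so restricting to ended events selects the shorter ones. The resulting bias is always towards short, quickly reversible toxicity, and it grows as the unresolved share grows.

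Long events are plausible here. Treatment has no maximum duration (Protocol section 4.2), and Protocol section 6.8.3.1 expects blood pressure to fall when cediranib is stopped or reduced, which implies that hypertension can last as long as dosing does. At stake is the accuracy of one tolerability description in the study report: a reader who takes the tabulated median as the typical duration of a persistent AESI would be misled.

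The plan handles the same problem differently elsewhere. Duration of response (SAP sections 3.2.2 and 4.2.7.2) and time to CA-125 progression (section 4.2.9) are both Kaplan-Meier analyses with censoring.

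**Working it through.** The plan states no figure for AESI duration or for the unresolved share, so there is nothing to reproduce. I take the statistic as a per-event duration.

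**Mechanism.** Let T be the event duration (median m) and C the time from onset to the end of observation (median c), both exponential and independent. The table uses T only when T < C. Then:

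- median of T among ended events = 1/(1/m + 1/c) = mc/(m + c)
- proportion ended = c/(m + c)

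The ratio of the ended-only median to m is also c/(m + c), so in this model the understatement equals the unresolved share. Examples, with m and c assumed:

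- m = 7, c = 120: 840/127 = 6.6 days, 94% ended, 6% too short
- m = 60, c = 240: 14,400/300 = 48 days, 80% ended, 20% too short
- m = 90, c = 120: 10,800/210 = 51 days, 57% ended, 43% too short
- m = 180, c = 120: 21,600/300 = 72 days, 40% ended, 60% too short

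**Simulation tied to the trial's timing** (400,000 events per scenario).

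From the documents:
- cut-off 8 months after the last first dose (SAP section 1.2)
- median OS 12 months and median PFS 6 months (SAP section 1.3), the latter used as a stand-in for time on treatment
- 12 months' accrual as originally planned (SAP section 1.3)

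Assumed:
- 22 months' accrual as an alternative
- exponential times
- onset uniform over treatment, or within the first 28 days
- event duration independent of death and of stopping treatment
- true median durations of 7, 30, 90 and 180 days

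Potential follow-up is F ~ Uniform(8, 8 + accrual) months. Treatment time is truncated at min(OS, F). An event counts as ended if onset + duration ≤ E, where either:

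- (a) E = min(OS, F), that is, follow-up to resolution until death or cut-off; or
- (b) E = min(OS, F, last dose + 30 days).

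Understatement = 1 - (ended-only median / true median). Ranges are over the two accrual lengths and two onset patterns.

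| True median (days) | (a) unresolved | (a) ended-only median (days) | (a) understated by | (b) unresolved | (b) ended-only median (days) | (b) understated by |
|---|---|---|---|---|---|---|
| 7 | 4-6% | 7 | 3-5% | 4-7% | 7 | 3-6% |
| 30 | 10-17% | 26-28 | 8-14% | 17-28% | 21-25 | 18-29% |
| 90 | 23-35% | 61-70 | 22-32% | 41-56% | 36-51 | 43-60% |
| 180 | 39-52% | 87-109 | 39-51% | 59-72% | 45-71 | 61-75% |

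**What the other displays supply.** The ongoing summaries describe the excluded events but do not change the duration statistic. Prevalence plots and per-patient grade plots can show unresolved events but yield no summary duration. The SAP does not say whether the life tables concern onset or resolution. The remaining AESI groupings, such as nephrotic syndrome, MDS/AML and pneumonitis, do not get these extra displays.

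**A gap in the ongoing categories.** The SAP names ongoing at death and ongoing at cut-off. It does not say where it puts an event whose follow-up stopped because it was judged unlikely to resolve, because new treatment began, or because the patient withdrew or was lost. The first of these is likely to include some of the longest events.

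**The case against.** The SAP states the restriction openly and, in the same sentence, pairs it with reporting of the events left out. The four common AESIs get further displays in which unresolved events can be seen, outcomes are tabulated, and every AE is listed. A reader might infer that ongoing toxicities disappear from the report. The documents do not support that: they leave one statistic only, and long events that end before cut-off stay in it. Nor do the documents support the inference that the ongoing summaries are bare counts, since the SAP says only that they are summaries.

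The size is also open to challenge. Protocol section 6.8.4.3 describes olaparib nausea and vomiting as mostly low grade and intermittent, and section 6.8.3.2 calls for early treatment of diarrhoea. Short events carry little bias. The stated safety objective does not name duration, and for rare AESIs in about 60 patients any median may rest on very few events.

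A simple Kaplan-Meier remedy has weaknesses too. With 57% OS events expected, death is a competing event rather than ordinary censoring. Repeated events within a patient are not independent. Censoring at 30 days after last dose would discard end dates obtained later under Protocol section 6.3.2.

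All of this stands as a limit on severity and on the form of the fix. It does not remove the defect: no planned summary is specified as a duration estimate that includes unresolved events.

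**Conclusion.** The concern holds in a limited form. As a measure of AESI duration, the planned statistic is biased downward for persistent events, and the accompanying displays do not correct it. With follow-up to resolution, the bias is negligible for events lasting about a week, modest at a month and material at three months or more. It is larger at a month and beyond if end dates stop at 30 days after last dose.

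The percentages rest on assumed durations, exponential times and independence. Independence is doubtful for an event such as hypertension, which may ease when dosing stops. A reader might take a single broad figure, such as 20-60%, as the bias for AESIs in general. That would be wrong: the mechanism examples giving that span all assume true medians of 60 to 180 days, and the documents supply none.

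Severity is minor. ORR, the futility rule and the other efficacy analyses are unaffected.

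**What to change.** In SAP section 4.2.9:

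- For AESI groupings with enough events, and at least for diarrhoea, fatigue, hypertension and nausea, add a time-to-resolution summary of the first event per patient. Censor unresolved events at last AE follow-up or data cut-off, whichever is earlier. Treat death as a competing event and report the cumulative incidence of resolution. Kaplan-Meier censored at death is an acceptable alternative if that assumption is stated.
- Label the existing duration table as resolved events only, and show the number (%) unresolved beside it. Include events whose follow-up ended for reasons other than death or cut-off.
- State whether the ongoing summaries give counts, elapsed duration or both, and whether the life tables are for onset or resolution.

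The cost is SAP wording and one more table per grouping. No new data are needed, because start and stop dates and outcome are already collected (SAP section 3.3.3). Reported durations will look longer, and a first-event analysis leaves recurrences to the existing displays.
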